3.6.5 Oncological outcome

Oncological outcome after 12 months (categorical outcome) will be classified into four categories according to the following definition:

1. PSA persistence
PSA \geq 0.2 at visit 2
2. Biochemical recurrence
PSA $<$ 0.2 at visit 2
AND
(PSA \geq 0.2 at visit 3 **OR** PSA \geq 0.2 at visit 4)
3. Early salvage treatment
PSA $<$ 0.2 at each of visit 2, visit 3, and visit 4

AND

Received adjuvant treatment* in the first year

4. Other (No recurrence or treatment)

PSA<0.2 at each of visit 2, visit 3, and visit 4

AND

No adjuvant treatment* in the first year

*Adjuvant treatment is defined as any adjuvant cancer treatment during the first year after surgery, as recorded on the study questionnaire at visit2, visit3 and visit4, under the question “Did the subject have any or have any adjuvant therapy planned?”. Common adjuvant treatment could include Hormonal Treatment or Radiotherapy.

Handling of partially missing information for oncological outcome

Participants with no adjuvant treatment reported will be considered as not receiving adjuvant treatment. Missing treatment date will be handled as discussed above (see section 3.3).

Participants with undefined oncological status due to missing PSA values will be reviewed case by case. If a participant has a PSA below 0.2 at a visit and has not started treatment since, we will assume previous PSA values were below 0.2. We will also use the later available PSA values (visit 5, part of the longer-term follow-up) to apply this rule.

For patients who died during the 12 months follow-up, we will report their oncological status before death (if available) but indicating that these patients have died, with the reason of death.

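### The SAP 3.6.5 rule for filling in missing PSA values, read literally, checks for treatment after the low PSA, when only treatment before it matters; some treated men can be put in the wrong oncological category

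*SAP*

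**What the plan says.** SAP 3.6.5 sorts men into four categories from the PSA at visits 2, 3 and 4 (3, 6 and 12 months):

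1. PSA persistence: at or above 0.2 at visit 2.
2. Biochemical recurrence: below 0.2 at visit 2, then at or above 0.2 at visit 3 or visit 4.
3. Early salvage treatment: below 0.2 at all three visits, and "Received adjuvant treatment* in the first year".
4. Other, with neither recurrence nor treatment: below 0.2 at all three visits and no treatment in the first year.

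The treatment window is explicit: "Adjuvant treatment is defined as any adjuvant cancer treatment during the first year after surgery". Silence counts as no treatment: "Participants with no adjuvant treatment reported will be considered as not receiving adjuvant treatment".

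For missing values the SAP first says "Participants with undefined oncological status due to missing PSA values will be reviewed case by case". It then gives one rule, for any man who "has a PSA below 0.2 at a visit and has not started treatment since, we will assume previous PSA values were below 0.2". It extends that rule to the 2-year visit: "We will also use the later available PSA values (visit 5, part of the longer-term follow-up) to apply this rule".

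SAP 4.9.4 reports the categories as frequencies and percentages by arm, with no test. SAP 3.3 says that all PSA data are used so that as many oncological failures as possible are captured.

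**The concern.** The rule reasons backwards in time: a low PSA now is taken to mean that earlier, unseen values were low. What can break this inference is treatment between the unseen value and the low one, because a raised PSA can fall once treatment starts. Treatment begun after the low PSA says nothing about earlier values. As written, *since* attaches most naturally to the visit with the low PSA. The rule then leaves out the condition it needs and imposes one that is irrelevant.

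At stake is the SAP's 12-month PSA-based report of cancer control by arm. The protocol (5.1) hypothesises equal cure rates, and SAP 1.2.2 lists oncological outcome at 12 months as a secondary objective. With no test planned, readers will rely on the counts. Two analysts who read *since* differently could also classify the same man differently, which a pre-specified rule should prevent.

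**Working it through.** The documents give no figure to reproduce here, so the check is one of logic, followed by a size range under stated assumptions.

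**Four cases under the literal rule.** Visits 2 to 5 are taken at months 3, 6, 12 and 24.

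| Case | Visit 2 | Visit 3 | Visit 4 | Treatment starts | Visit 5 | True category | Category assigned |
|---|---|---|---|---|---|---|---|
| A | <0.2 | <0.2 | missing, truly ≥0.2 | month 15 | <0.2 | 2 | 4 |
| B | <0.2 | missing, truly ≥0.2 | <0.2 | month 9 | <0.2 | 2 | 3 |
| C | missing, truly ≥0.2 | ≥0.2 | <0.2 | month 9 | <0.2 | 1 | 2 |
| D | missing, truly <0.2 | <0.2 | <0.2 | month 15 | ≥0.2 | 4 | none |

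- A: no treatment follows visit 5, so visit 4 is filled as low. Treatment fell after the first year, so the man reaches category 4.
- B: no treatment follows visit 4, so visit 3 is filled as low. First-year treatment puts him in category 3.
- C: visit 2 is filled as low, so true persistence becomes recurrence.
- D: a sound fill from visit 3 or visit 4 is refused because treatment came later.

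**All patterns.** I listed every combination of true PSA state (below 0.2, or at or above it) at visits 2 to 5, with treatment starting never or at month 4.5, 9, 15 or 26. A raised PSA could fall only after treatment. At least one PSA was missing at visits 2 to 4, and visit 5 was always observed. I kept the 192 patterns that the observed values alone leave undefined. I then applied (i) the literal rule, with no treatment after the low PSA, and (ii) the alternative, with no treatment before it.

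| True category | Patterns | Literal: right / wrong / undetermined | Alternative: right / wrong / undetermined |
|---|---|---|---|
| 1 Persistence | 44 | 0 / 17 / 27 | 0 / 0 / 44 |
| 2 Recurrence | 78 | 10 / 12 / 56 | 5 / 0 / 73 |
| 3 Early salvage | 28 | 20 / 0 / 8 | 2 / 0 / 26 |
| 4 Other | 42 | 17 / 0 / 25 | 26 / 0 / 16 |
| All | 192 | 47 / 29 / 116 | 33 / 0 / 159 |

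Under the literal rule:

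- 12 recurrence patterns lose that label: 6 go to category 3 and 6 to category 4.
- 17 persistence patterns move: 7 to category 2, 9 to category 3 and 1 to category 4.

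The alternative makes no wrong assignment but leaves 159 − 116 = 43 more patterns undetermined. These are counts of logical patterns, not of patients, and they carry no frequency.

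**Size.** The documents give no 12-month recurrence rate and no PSA missingness rate. Protocol 13.7 lists adjuvant therapies at 30%, but with no time frame and not as a recurrence rate. As assumptions, take true recurrence of 5% to 15% and the decisive PSA missing in 5% to 20% of those men.

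Men exposed per arm = men per arm × recurrence rate × missing rate.

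- 364 / 2 = 182 per arm: 182 × 0.05 × 0.05 = 0.5, up to 182 × 0.15 × 0.20 = 5.5.
- 404 / 2 = 202 per arm: 202 × 0.05 × 0.05 = 0.5, up to 202 × 0.15 × 0.20 = 6.1.

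For recurrences these are upper bounds, because they suppose that every exposed man was treated and then had a low PSA. Misplaced persistence cases would be additional.

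**The case against.** **Another meaning of *since*.** The sentence follows one about missing PSA values, so *since* could mean since the missing visit, or since surgery. Either would make the rule sound. This stands as a possible intention, but the text states neither, and the literal reading gives wrong categories.

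**Case-by-case review.** A reviewer who sees treatment between the missing visit and the low PSA might stop. This stands in part: some errors may be caught, but the fill-in rule is the only criterion that the SAP gives for the review.

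**Unlikely missingness.** SAP 3.3 applies no window to PSA dates, and protocol 7.2.2.2 increases testing when a low PSA is detectable. A man treated soon after month 12 would probably have a raised value on file. This makes case A less frequent, but not impossible.

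**Treated men remain visible.** A reader might infer that the rule hides treated recurrences altogether. It does not when first-year treatment was reported: men like case B appear by arm under early salvage treatment, mislabelled but visible. Category 4 is reached when treatment began after the first year, or when treatment was not reported.

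**Direction.** A reader might also infer that the error always flatters cancer control. Case C shows otherwise, since some persistence patterns move into recurrence. Nor do the documents show bias between arms, which would need missingness or treated recurrence to differ by arm.

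**Conclusion.** The point holds as a fault in the wording of a classification rule. Followed as written, it can put a treated recurrence into category 3 or 4, misplace PSA persistence (including into recurrence), and refuse some sound fills. It works against the aim of capturing failures in SAP 3.3.

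Its weight is modest. The outcome is descriptive and the IIEF-5 primary analysis is unaffected. The number of men is probably a few, on assumed rates that the documents neither support nor exclude. It would be tempting to say that the trial's case on cancer control fails with this table. The documents do not support that: margins are tabulated separately (SAP 4.9.1), the iDMC reviews oncological outcomes quarterly (protocol 13.1.1), and a 5-year oncological analysis is intended (protocol 6.2). The change is still worth making, because the error is clear and nearly free to remove.

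**What to change.** In SAP 3.6.5, replace the *since* clause with: *and had not started any cancer treatment between surgery and the date of that PSA (including a visit 5 PSA)*. If treatment did start in that interval and the observed values do not settle the category, leave the status undetermined after case review and report the number of such men by arm.

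Two details need attention:

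- When visit 5 PSA is used, treatment data up to visit 5 must be read with it. Protocol 7.4 schedules both at 2 years, but the SAP 3.1 summary of 2-year data lists only questionnaires, so confirm that the treatment records are in the extract.
- SAP 3.3 can set a missing PSA date and a missing treatment date to the same expected visit. Where an imputed date decides which came first, treat the order as unknown.

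The cost is a few words and a date comparison on data already planned for collection. The downside is that a few more men stay unclassified, including some whom the present rule happens to classify correctly. Their observed data cannot distinguish them from men with a treated recurrence, so a visible undetermined count is the more accurate report.

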3.6.6 Positive Surgical Margins (PSM)

Participants surgical margins will be classified into three categories according to the following definition:

1. Negative surgical margins

No positive surgical margins

2. Small single positive surgical margin

Positive surgical margin in a single location

AND

Length of the positive margin is less than 3mm

3. Large or multifocal surgical margin

Positive surgical margin in at least two locations

OR

Length of any positive margins at least 3mm

Handling of missing PSM information

Any participant who was operated but do not have PSM data, or sufficient data to be classified into one of the three categories will be considered as missing.

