#### 10.1.1 Control Arm: Standard RARP

Standard RARP (control arm) is performed as per NHS routine practice at participating regional uro-oncology sites. Pre-operative parameters used to guide surgeon Nerve Spare (NS) decision include mpMRI NS planning sheet prepared in conjunction with a consultant genito-urinary radiologist, prostate biopsy tumour histology information and digital rectal examination under general anaesthesia. Individual surgeons are asked after RARP to grade the quality of NS performed on each side numerically as seen below (25):

- Grade 0 - No nerve spare. Wide excision of lateral pelvic fascia (LPF) and Denonvilliers' fascia.
- Grade 1 - Limited nerve spare, or partial/incremental nerve spare. Incision through outer compartment of LPF.
- Grade 2 – Interfascial nerve spare. LPF is taken just outside the layer of the veins of the prostate capsule. Still largely preserving the large neural trunks (also known as the NVBs).
- Grade 3 – Intrafascial nerve spare. LPF is taken just outside the prostate capsule. Represents greatest possible NS.

NeuroSAFE PROOF collects detailed information on histological surgical margin status for safety and future publication purposes. Descriptions of histological diagnosis can differ between sites due to varying interpretations of histological analyses. In line with quality assurance, we will request anonymised pathology reports to ensure accurate, standardised reporting in the trial database. This will occur across both arms of the trial.

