#### 10.1.2 Intervention Arm: NeuroSAFE RARP

NeuroSAFE RARP (intervention arm) will be performed in accordance with previously described methods, initially developed at the Martini Clinik, Hamburg, Germany. All patients in the NeuroSAFE arm will undergo initial bilateral NS where technically possible. The procedure differs from standard RARP in that initial insertion of the robotic camera port is through a modified incision using the Alexis Laparoscopic System (Applied Medical, Rancho Santa Margarita, CA).

Once the specimen is disconnected from its attachments, the specimen can be removed from the patient through the protected incision immediately.

Pneumoperitoneum can be re-established quickly by placing the laparoscopic cap back on the Alexis.

The specimen will then be painted by the operating surgeon (sites may differ, but at UCLH; yellow for left and green for right side of the prostate). The painted areas can be sprayed with a fixative spray if site prefers (to prevent ink running). The specimen will be delivered expediently to the pathology laboratory where frozen section analysis of the painted areas will be undertaken. Whilst this analysis is taking place the robot will be re-docked and pneumoperitoneum established. The robotic instruments will be reinserted. The surgeon will proceed to fashion the urethro-vesical anastomosis and perform a pelvic lymphadenectomy (where indicated) whilst the result of the frozen section analysis is awaited.

Upon delivery of the prostate gland to the pathology lab, a sharp blade will be used to remove the pre-painted surface of the gland (which had been in contact with the neurovascular bundles). The tissue sample will be snap frozen and embedded in OCT. Using a cryostat, 10-micron thick slices will be placed on slides. The entire length of the area of interest will be sampled in this way generating an average of 5 frozen sections per side and approximately 10 in total. The slides will be stained with H&E and will be examined by a consultant pathologist. As soon as examination is complete the pathologist will telephone the operating surgeon to give the result. On frozen section analysis, presence of cancer cells at the inked surface margin of the specimen constitutes a positive margin and the length of any positive surgical margin will be recorded.

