4.9 Descriptive outcomes analysis

4.9.1 Positive Surgical Margins

The PSM will be reported descriptively, reporting the number and percentage of participants in each of the PSM category, by arm.

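### SAP 3.6.6 turns some known positive surgical margins into missing values and never does so to known negatives, so the reported positive share is biased downward if any such cases remain at analysis

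*SAP*

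**What the plan says.** SAP 3.6.6 sorts each operated man into one of three margin categories.

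- Category 1 (negative) rests on one fact: "No positive surgical margins".
- Category 2 (small and single) needs two facts joined by AND: "Positive surgical margin in a single location" and "Length of the positive margin is less than 3mm".
- Category 3 (large or multifocal) needs either of two facts joined by OR: "Positive surgical margin in at least two locations", or any positive margin of 3 mm or more.

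The rule for incomplete information covers operated participants who "do not have PSM data, or sufficient data to be classified into one of the three categories will be considered as missing".

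The analysis in SAP 4.9.1 is descriptive, "reporting the number and percentage of participants in each of the PSM category, by arm". It includes no test and does not state the denominator. SAP 3.9.4 lists positive margins among the pathology results but refers back to 3.6.6, so no separate yes/no variable for any positive margin is defined. SAP 4.6 places missing-data frequencies for all variables in an appendix. It does not say that a positive margin of unknown extent will be shown apart from a man with no margin data.

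**The concern.** The three categories ask for different amounts of information. A pathologist's statement that the margin is clear is enough for category 1. A statement that it is positive is not enough for category 2 or 3, because extent is needed as well. Incomplete extent data can therefore remove a man from the table only if he is already known to be positive, so the missingness depends on the outcome itself.

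This differs from the SAP's handling of partial data elsewhere. Partly completed IIEF-5 forms are kept and scored conservatively (3.4). Unclear oncological status is reviewed case by case (3.6.5). PSA values are used without a time window so that oncological failures are not missed (3.3). The margin rule instead discards an adverse finding that is already known.

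The table matters because the protocol's lay summary presents the technique as a way to extend nerve sparing without leaving more cancer at the margin. Margins are also a secondary endpoint in Protocol 7.2.2.5, and Protocol 10.1.1 says margin data are collected partly for safety. A reader will look at this table for reassurance on cancer control.

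**Working it through.** **Step 1: apply the rule to every pattern.** The inputs are the definitions in SAP 3.6.6. Category 1 needs no extent data. For men known to be positive:

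| Number of positive sites | Length <3 mm | Length ≥3 mm | Length unknown |
|---|---|---|---|
| One | category 2 | category 3 | **missing** |
| Two or more | category 3 | category 3 | category 3 |
| Unknown | **missing** | category 3 | **missing** |

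Five of these patterns are incomplete. Three become missing. Two stay positive, because either condition of category 3 is enough alone. No known negative is lost in this way.

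**Step 2: direction of the bias.** Let p be the true positive share among operated men with a known margin status, and m the share of those positives that cannot be classified.

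- Missing men left out of the denominator: reported share = p(1 − m)/(1 − pm). Since p < 1 and m > 0, 1 − m is smaller than 1 − pm, so the result is below p.
- All these men in the denominator: reported share = p(1 − m), which is also below p.

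**Step 3: size.** The documents state no margin rate and no rate of missing extent, so there is no figure to reproduce. The ranges below are assumptions. Each cell gives the reported positive share with missing men excluded / with all men in the denominator.

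| True p | m = 5% | m = 10% | m = 20% | m = 30% |
|---|---|---|---|---|
| 10% | 9.5 / 9.5 | 9.1 / 9.0 | 8.2 / 8.0 | 7.2 / 7.0 |
| 20% | 19.2 / 19.0 | 18.4 / 18.0 | 16.7 / 16.0 | 14.9 / 14.0 |
| 30% | 28.9 / 28.5 | 27.8 / 27.0 | 25.5 / 24.0 | 23.1 / 21.0 |
| 40% | 38.8 / 38.0 | 37.5 / 36.0 | 34.8 / 32.0 | 31.8 / 28.0 |

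In counts, take one arm at the recruitment target of 202 (SAP 1.4), for illustration only. With 61 positives the true share is 61/202 = 30.2%. If 12 of the 61 cannot be classified, the table shows 49/190 = 25.8%, or 49/202 = 24.3% on the full denominator. The 141 negatives appear as 141/190 = 74.2% or 141/202 = 69.8%, so the negative share rises only under the first denominator.

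**Step 4: the arms.** With equal p and equal m the false difference is zero. If p = 30% in both arms and m is 20% in one and 5% in the other, the arms show 25.5% and 28.9%, a false difference of 3.4 points. With the full denominator it is 28.5 − 24.0 = 4.5 points. The contrast in m is an assumption without support in the documents.

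**Step 5: the split among positives.** Multifocal margins are never lost, while single ones of unknown length are. The split among classified positives can therefore also move towards the large or multifocal category.

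**The case against.** The strongest reply is that the gap may never matter in practice. SAP 2.4 provides for missing-data checks before analysis, with queries to sites, and a positive margin without a length is an obvious query. Protocol 13.2 has pathology reports from both arms reviewed against a reporting procedure. The margin groups in Protocol 7.2.2.5 already use cut-offs of 1 mm and 3 mm, so length is needed in both arms anyway. All of this stands as a reason to expect few cases. It does not change what the rule does to those that remain.

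SAP 4.6 could also be read as covering the point: if status, number of sites and length are tabulated as separate variables, positives without a length would be visible. That is possible, but the SAP does not list them separately, and the table in 4.9.1 would still omit these men.

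Some stronger readings are tempting and should be resisted.

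- *Any positive margin lacking a length or a site count is lost.* It is not. Two or more sites, or a length of at least 3 mm, is enough for category 3.
- *The negative percentage is inflated.* That depends on a denominator that 4.9.1 does not state.
- *The arms will be distorted unequally.* For the NeuroSAFE arm, Protocol 10.1.2 says "the length of any positive surgical margin will be recorded", but this concerns the frozen section, and SAP 3.6.6 does not say that it feeds the margin category. Protocol 10.1.1 says "Descriptions of histological diagnosis can differ between sites due to varying interpretations of histological analyses", but that is about interpretation rather than absent lengths, and the same section promises standardised reporting in both arms. Randomisation is stratified by site (SAP 1.5), which tends to balance site differences.

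Finally, sampling error is larger than the example in step 4 with missing men excluded: at 30% and 202 men per arm, the standard error of an arm difference is √(2 × 0.3 × 0.7/202) = 4.6 points, against 3.4. That limits the practical weight of the point, but a systematic error that costs almost nothing to remove need not be kept.

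**Conclusion.** The defect follows from the wording of SAP 3.6.6 alone: three patterns of known positive margin become missing, no known negative does, and no any-positive count is defined to recover them. If at least one such man remains at analysis, the positive share among men with known status is understated.

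A reader might infer that the margin table will be wrong, or will favour one arm. The documents do not support that, because they give no frequency for these cases and no reason to expect them more in one arm. Across the assumed ranges (p from 10% to 40%, m from 5% to 30%), the shortfall runs from about half a point to 8.2 points with missing men excluded, and up to 12 points on the full denominator. Those sizes rest on the assumptions and are not predictions. Men with no margin status at all are a separate matter, and their effect depends on who they are.

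Margins are descriptive and untested, so the primary outcome, power and type I error are untouched. The change is worth making before analysis, but it is a correction to one reporting rule.

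**What to change.** In SAP 3.6.6 and 4.9.1:

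1. Report any-positive versus negative by arm for all operated men with a known margin status.
2. Divide the positives into small single, large or multifocal, and a new row *positive, extent not recorded*.
3. Reserve *missing* for men with no margin status, and show that count by arm beside the table.
4. State the denominator of the percentages.

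The cost is about one sentence and one table row. No new data are needed. The reported rate of positive margins may be slightly less favourable than under the present rule.
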